## **10. Medical treatment and protection of subjects**

### **10.1 Risk assessment of subjects in the study and risk disposal measures and plans**

(1) Reporting method: Any adverse event, such as the subject's subjective discomfort and abnormal laboratory test, shall be treated seriously, analyzed carefully, and immediately taken measures to protect the safety of the subject.

(2) Processing procedures: record in detail, retest according to the situation, and record its duration, return, disappearance, etc.

(3) Unmitigated adverse events should be followed up, and all adverse events should be followed up until they are properly resolved or stable.

### **10.2 Medical treatment and protection of subjects during the study**

The subjects' rights and welfare will be protected during the study, and it is

stressed that the quality of their medical care will not be affected by their refusal to participate or withdrawal from the study. If a patient withdraws from the study, we will no longer perform tests related to the study. The Investigator will provide insurance for the subjects participating in the study program, and the subjects will receive timely and free treatment if they suffer damage related to the study, and will be compensated or compensated in accordance with laws, regulations and mutual agreements.

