### **1.4.2 Probability of injury**

the possibility of subject harm may involve adverse effects associated with levosimendan. Clinically possible adverse effects are increased heart rate or temporary and slight decrease in blood pressure, which can be treated with dose reduction or withdrawal and symptomatic management.

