#### **4.5 Criteria for subject withdrawal**

Early withdrawal All patients who fill in the informed consent form and are screened for qualified randomized entry into the trial are referred to as shedding cases

(shedding and excluding cases should be controlled below 20% of the total number of cases), no matter when they quit for any reason, as long as they do not complete the observation period specified in the scheme. The reasons are as follows: (1) The investigator considered it most beneficial for the patient to terminate treatment due to safety concerns (such as adverse events); (2) Serious protocol violations (any protocol violations will be assessed by the investigator, who will consult the principal investigator of the group leader unit to determine whether they are serious enough to warrant withdrawal from the study); (3) Patients voluntarily terminate the study. Patients are free to terminate the study under any circumstances and will not be discriminated against in their subsequent treatment.

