## 6. Research steps

- (1) Patients eligible for inclusion in the study were screened and informed consent was signed.
- (2) Patients were randomly assigned to the experimental group or the control group. Vital signs and hemodynamic parameters were recorded 1 hour before administration, and related indexes such as cardiac function and pulmonary circulation were detected by transesophageal ultrasound, as well as arterial blood gas, central vein blood gas, blood routine, liver and kidney function, electrolyte, myocardial enzyme profile and BNP were detected by blood sampling.
- (3) According to the study protocol, all subjects in the two groups began administration at 8am, and 8am vital signs, arterial blood gas, central vein blood gas,

blood routine, liver and kidney function, electrolytes, myocardial enzyme profile and BNP during medication period and the first 24 hours after medication completion were recorded. The related indexes of cardiac function, pulmonary circulation and hemodynamics were monitored by transesophageal ultrasound. Study withdrawal/early termination: Family members refuse to continue treatment if: Family members withdraw from the study; In the presence of experimental-related serious adverse reactions.

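### Read together, sections 4.5, 6 and 10.2 would leave patients withdrawn for safety or a serious protocol violation without the 48h TEE behind the primary outcome

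*Protocol*

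**What the plan says.** Three sections of the protocol bear on this point.

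- **Section 4.5 (withdrawal criteria).** A randomised patient is a shedding case, whatever the reason, "as long as they do not complete the observation period specified in the scheme". The first listed reason is: "The investigator considered it most beneficial for the patient to terminate treatment due to safety concerns (such as adverse events". The second is serious protocol violations, which the investigator assesses with the lead unit's principal investigator "to determine whether they are serious enough to warrant withdrawal from the study". The third is the patient's own decision to leave. The section also sets a ceiling: "shedding and excluding cases should be controlled below 20% of the total number of cases".
- **Section 6 (research steps).** A garbled item reads: "Study withdrawal/early termination: Family members refuse to continue treatment if: Family members withdraw from the study". It continues: "In the presence of experimental-related serious adverse reactions".
- **Section 10.2 (protection of subjects).** The consequence is stated without qualification: "If a patient withdraws from the study, we will no longer perform tests related to the study".

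The primary outcome is the RVD rate at 48h (sections 2 and 7.1). RVD is defined from echocardiographic measures, and the study uses TEE to obtain them (section 1.1.1). The infusion runs for 24h (section 5.1), so any permanent stop during it comes before the 48h assessment.

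**The concern.** The protocol does not separate two events: the study infusion ending, and the patient leaving the study. Sections 4.5 and 6 place investigator-led exits beside voluntary ones, and section 10.2 then ends study tests on withdrawal. On that combined reading, a patient taken off treatment for safety, or withdrawn for a protocol violation, has no 48h TEE and so no primary outcome.

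These losses occur after randomisation, for reasons that may depend on the arm. Section 1.4.2 expects a raised heart rate or a small fall in blood pressure with levosimendan. Control patients can also be lost, because ventilated ARDS patients can have safety problems from any cause. If the arms lose different numbers, and the patients lost differ in RVD rate from those kept, the comparison among observed patients no longer estimates the randomised effect.

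This is a rule about data collection, so it belongs in the protocol. An analysis plan can choose how to treat a missing value, but it cannot recover a TEE that was never done.

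**Working it through.** **1. The passages side by side**

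| Event | Where it is placed | Study tests afterwards |
|---|---|---|
| Treatment ended by the investigator for safety | 4.5, withdrawal criteria, reason 1 | Stop, if 10.2 applies |
| Serious protocol violation | 4.5, reason 2, explicitly withdrawal from the study | Stop, if 10.2 applies |
| Trial-related serious adverse reaction | 6, withdrawal or early-termination item | Stop, if 10.2 applies |
| Patient or family leaves | 4.5, reason 3; 6 | Stop under 10.2 |
| Temporary pause or rate reduction | 5.1 | Not classed as withdrawal |

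The only follow-up expressly continued after an event is that of adverse events (sections 8 and 10.1). No passage says that the 48h TEE is still done after the infusion is permanently ended. The vocabulary does not settle the matter: section 1.4.2 uses withdrawal for stopping the drug, "which can be treated with dose reduction or withdrawal and symptomatic management".

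**2. The plan's own figures**

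Section 3.2 gives a mean difference of 20%, SD 20%, two-sided alpha 0.05 and power 0.9. The t-test solution is 22.02 per arm, which rounds up to the stated 23. With 20% shedding, 23/0.8 = 28.75, rounded up to 29 per arm or 58 in total. Both figures reproduce. This allowance replaces lost numbers; it does not protect against selective loss. The ceiling in 4.5 is 0.20 × 58 = 11.6, so below 20% means at most 11 patients, for all reasons together and in any split between arms.

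**3. Illustration of the bias**

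The protocol gives no expected 48h RVD rate and no rate of permanent stops. The following are therefore assumptions: 29 per arm, no true effect, the same true RVD rate p in both arms, analysis of observed patients only, L patients lost in an arm, and a share q of those lost having RVD.

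Observed rate = (29p − qL)/(29 − L)

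With p = 0.60 (29p = 17.4) and q = 1:

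- L = 0: 17.4/29 = 0.600
- L = 1: 16.4/28 = 0.586
- L = 3: 14.4/26 = 0.554
- L = 6: 11.4/23 = 0.496

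The chance of a false significant benefit was found by exact enumeration (two-sided 0.05, levosimendan lower, unstratified tests).

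| Lost, levosimendan v control | Spurious difference | False benefit, chi-square (Fisher) |
|---|---|---|
| 0 v 0 | 0 points | 2.3% (1.2%) |
| 3 v 3 | 0 points | 2.9% (1.6%) |
| 3 v 1 | 3.2 points | 4.2% (3.0%) |
| 3 v 0 | 4.6 points | 7.0% (4.0%) |
| 6 v 0 | 10.4 points | 12.4% (11.4%) |

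**4. Sensitivity to the assumptions**

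When only one arm loses patients, the spurious difference reduces to L(q − p)/(29 − L).

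- Varying p with q = 1: for 6 v 0, p = 0.50 gives 6 × 0.50/23 = 13.0 points and p = 0.80 gives 6 × 0.20/23 = 5.2 points. For 3 v 0, the same rates give 3 × 0.50/26 = 5.8 and 3 × 0.20/26 = 2.3 points.
- Varying q with p = 0.60 and 6 v 0: q = 0.8 gives 6 × 0.2/23 = 5.2 points in favour of levosimendan, q = 0.6 gives none, and q = 0.4 gives 5.2 points against it.

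**The case against.** The strongest reply is that this is an ambiguity and that the harmless reading has real support. The sentence in 10.2 has the patient as its subject and follows an assurance that refusing or leaving will not affect care; section 11.1 uses the same language for the relatives' right to leave. Section 4.5 speaks of ending treatment in its first reason and of ending the study in its third, and defines shedding by an incomplete observation period. A patient off the infusion who still has the 48h TEE would not meet that definition. Section 6 never mentions ending treatment, and its sentence is garbled. Patients with adverse events remain under follow-up (sections 8 and 10.1). Exposure is also narrow: section 5.1 provides for reduction, interruption and restart, and sections 1.4.2 and 1.4.3 describe the expected effects as mild.

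All of this stands as far as it goes. It shows that the adverse reading is not the only one. It does not show that the TEE is done: 10.2 is not limited to voluntary withdrawal, the second reason in 4.5 is withdrawal from the study in terms, and adverse-event follow-up promises no TEE. Three centres could act differently in good faith.

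A reader might infer more than the documents support:

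- *That the protocol orders the 48h TEE to be skipped after every safety stop.* It does not; that result comes only from joining the sections.
- *That temporary pauses under 5.1 cost outcome data.* Nothing suggests this.
- *That mortality follow-up ends.* Section 10.2 stops tests and does not mention vital status.
- *That the result will favour levosimendan.* The direction depends on who is lost, which the documents do not show.
- *That the 4.5 ceiling measures the likely bias.* A split of 9 v 2 with every lost patient having RVD would give 0.570 − 0.420 = 15.0 points. That is an extreme bound which uses the whole allowance, set for losses of every kind.

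**Conclusion.** The point holds as a conflict in the withdrawal rules that should be fixed, with medium confidence about how sites would read them. As written, the protocol can remove the primary outcome from randomised patients for reasons that may depend on the arm, and no statement prevents this.

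The size cannot be estimated from the documents. The 4.6 points (3 v 0) and 10.4 points (6 v 0) rest wholly on an assumed 60% RVD rate, no true effect, one-sided loss, every lost patient having RVD, and analysis of observed patients only. The protocol names a full analysis set without saying how a missing 48h outcome is handled, so that last assumption may not match the analysis plan. Equal loss gives no bias under these assumptions, nor does loss unrelated to RVD. What does not depend on the illustration is that a TEE not done at 48h cannot be recovered later.

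**What to change.** Reconcile sections 4.5, 6 and 10.2:

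- State that ending the study infusion, or a protocol violation, does not by itself end outcome collection.
- Limit the sentence in 10.2 to refusal of further data collection by the patient or family.
- Add, for example: *In every randomised patient the planned 48h TEE (where feasible) and 28-day and in-hospital vital status are collected, unless the patient or family refuses further data collection.*
- Record the reason whenever a 48h TEE is not done.

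Leave the criteria for ending treatment unchanged; they are a clinical matter and not part of this point.

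The cost is protocol wording in three sections, with no new procedure. The downside is that a few TEEs already planned will be done in patients off study drug, and some may not be feasible.

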### **10.3 Medical Treatment and Protection of Subjects after the study**

The patient will continue to receive routine treatment after the study is completed. Subjects shall not be required to waive their right to free treatment and compensation for research-related damage.

## **11. Supporting documentation and notes**

### **11.1 Informed Consent Process**

Informed consent is given before the subject's relatives agree to participate in the study and continues throughout the study. Informed consent With the consent of the Ethics Committee, relatives of the subject should read the informed consent. The researchers explain the study process and answer questions from the subjects' relatives; The subjects' relatives were informed of possible risks and their rights. Subject relatives may discuss with other family members or guardians before agreeing to participate. Researchers must inform their relatives that participation in the study is voluntary and that they may withdraw from the study at any time. Copies of the informed consent can be provided to relatives of the subjects for preservation. The rights and welfare of relatives of the subjects will be protected, and it is stressed that the quality of their medical care will not be affected by their refusal to participate in the study.

### **11.2 Privacy Protection**

The relevant data of the subjects shall be kept by the project quality controller, who shall store the relevant forms, records and samples. Under the condition that the

confidentiality principle and relevant regulations are not violated, the supervisors, ethics committee and inspectors of the drug regulatory department can access the original medical records, and any research information shall not be disclosed to unauthorized third parties without prior approval.

### **11.3 Collection and use of specimens and data**

The blood samples collected by the institute are only used for routine testing of medical tests during treatment, so no remaining samples will be retained. After the study, the retained images and other data will be used for future research with the consent of the subjects.

### **11.4 Quality Control and quality Assurance**

All physicians participating in this study should be familiar with the diagnosis and treatment of ARDS, right heart failure, and the use of transesophageal ultrasound. The CRF form needs to be checked by two people. The project quality control leader shall conduct weekly quality control on the study data to ensure the safety, accuracy and orderly conduct of the test.

### **11.5 Data processing and record saving**

#### **11.5.1 Data Collection and Management**

The required data were collected from the medical records of patients who met the inclusion criteria and filled in a paper case report form (CRF). Data collection will be conducted by clinical investigators under the supervision of the responsible person, who will be responsible for the accuracy, completeness and timeliness of the reported data. All data should be clear to ensure accurate interpretation and traceability. Data entry: After training the data entry clerk, remote data entry is carried out. Double entry method is adopted, which is completed independently by two people. Review of data: Manual comparison of data in the case report form and the database to ensure that the data in the database is consistent with the results in the case report form. Data locking: In addition to the data review as described above, the principal investigator, statistician, data manager and sponsor representative will further discuss and confirm

the main content of the study proposal and the statistical analysis proposal. Conduct an audit to confirm that all data has been entered into the database, all questions have been resolved, and the analysis population has been defined and judged to lock the data. Clinical data will be stored in a database, which should be password protected, and logic proofreading procedures should be set up when the database is established.

### **11.5.2 Study data retention**

The minimum retention time of all data and original documents studied is 1 year, and permission should be obtained before destruction.

### **11.6 Conflict of Interest Statement**

This study has no conflict of interest with any of the physicians involved in the clinical study.

